3.3.2.2. If interested they will be provided information about the study and will be allowed to proceed to the telephone interview. These techniques have been used successfully in previous VABHCS studies of yoga interventions.(59) The VABHCS Institutional Review Board (IRB) will pre- approve all forms of advertisement. Current VA policy does not allow email communications as part of the recruitment procedures. Sample size calculations, based on power analyses, require the following number of completers equally divided between the yoga and walking groups to test the hypotheses for each dependent variable: **n=70** completers to test Aim 1: Depressive Symptoms and Mood Scale; **n=56** to test Aim 2: GABA changes; and **n=68** to test Aim 3: RSA changes [D.20]. To meet the criteria for each Aim/Dependent Variable n=70 subjects will complete the intervention with n=56 having usable MRS data. Using data from Study 4, with consideration of changes in inclusion and exclusion criteria and research setting, the following recruitment schedule will be required during a 5-year study period, which will include over 4 years of recruitment and treatment. The required total recruitment and annual requirements at each stage are as follows: telephone screen=420 total or 105/year; screening interview=173 total or 43/year; randomization=100 total or 25/year; and completers=68 total or 18/year.

3.3.2.3. Participation in Non-Assigned Group: A Retention Plan: Prior to randomization, subjects will be asked their group of choice (i.e., yoga or walking), as not being assigned to a group of choice could influence dropout rate. In order to retain subjects not assigned to their choice, subjects will be allowed to participate in the group they are not assigned to for 16 sessions or 8 weeks (i.e., the second intervention), whichever comes first, if they complete their randomized intervention and 14 week follow up phone call. Retention in the randomized intervention is given priority over contamination of the 6-month follow up with the 2nd intervention. There will be no difference in how subjects in the randomized intervention or second intervention will be monitored during the first eight weeks of the intervention. Subjects will not be paid for class attendance or evaluations during the 2nd intervention nor will they undergo MRS scanning. These data are exploratory.

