- (23) Subject has been treated a) with a scheduled dose of anti-anxiety agents (e.g., benzodiazepines) or sleeping aids (e.g. Ambien or sedative hypnotics) or b) with pain medication other than Non-Steroidal Anti-Inflammatory Drugs (NSAIDS) in the last one month except for procedure related pain management (e.g., dental procedures).
- (24) Has greater than three current criteria for Alcohol or Substance Use Disorder using DSM-V criteria.
- (25) Does not have a period of 48 hours of no alcohol use on TLFB to participate in scanning given the effects of alcohol consumption on the GABA.
- (26) Has a neurologic condition, such as a Traumatic Brain Injury (TBI) with a loss of consciousness of greater than 30 min, that in the opinion of the PI could compromise subject safety or the integrity of the study.
- (27) Has a medical condition that in the opinion of the PI could compromise subject safety or the integrity of the study.
- (28) Subject would not be expected to complete the study including scheduling issues.
- (29) Has an Axis-I diagnosis, other than depression except as listed, that in the opinion of the PI would interfere with the subject's participation in this study.
- (31) Has participated in another research study in the last 3 months that could affect the dependent variables.
- (32) Must have a period of 24 hours of no nicotine use on TLFB to participate in scanning or nicotine use as allowed by CSD&R Project Manager.
- (33) Subject does not agree to study procedures designed to protect against COVID-19 and the requirements of the virtual interventions.

3.3.2.7. Randomization: Group assignments will be conducted using permuted block randomization with varying block sizes. Block sizes will be multiples of the number of treatments and take the allocation ratio into account. For this study with a 1:1 randomization of 2 groups (yoga and walking), block sizes will be 2, 4, and 6. Randomization will be computer generated with each randomization assignment put on a card in numerically labeled envelopes that will be sealed. The envelopes will be opened in sequential order at the time of randomization by a member of the staff that is not blinded to group assignment. Subjects who want more time to think about participation can be randomized within 12 days of the last screening assessment, with the interventions starting within 7 days.

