3.3.2.8. Group Assignment, & Blinding: All investigators are blind to group assignment prior to randomization. Blinding will be guided by the Cochrane Collaboration Tool for assessing risk of bias in randomized trials.(14) The study physicist, [name], and [name], the RSA expert, will be blind to group assignment. Investigators who administer subjective instruments (i.e., Hamilton Rating Scale for Depression and CAPS) will be blind to group assignment. Subjects will fill out self-reporting mood and psychological scales in paper form that will be entered into the VA network by research staff. All VA paper documents with sensitive information will be secured in a locked filing cabinet in a designed VA Office. ECG data used for RSA analysis and MRS data will be labeled with a blinding code provided by the Data Coordinating Center, such that ECG data and MRS data are stripped of identifying information, including removal of study ID, date of acquisition and timing of the assessment (baseline, pre or post the intervention at weeks 4, 8, or 12) before being sent [name] for analysis. As subjects are not blind to the intervention, there is no procedure to break the blind for clinical reasons.

3.3.2.9. Gender Differences: While we will equally recruit both genders, due to the demographics of the VABHCS population, it is anticipated that more males will be recruited, which will provide much needed information on the efficacy of this intervention in men. Due to the influence of menstrual cycle phase and associated changes of progesterone on brain GABA/Cr levels, serum levels of progesterone will be drawn before each scan, with progesterone levels less than or equal to 1.3 ng/ml being considered the non-luteal stage, a stage when GABA/Cr is not influenced by menstrual cycle.(75) Serum progesterone levels will be drawn at the VABHCS.

3.3.2.10. Subject Compliance and Payment: Compliance with group session attendance and homework is important, both as an assessment of treatment acceptance and as a measure of the "dose" of the intervention required for symptom reduction. Attendance at the interventions will be recorded on an attendance sheet; home practice of yoga and walking will be recorded on the weekly PAR. Subjects will be paid for their time: \$10 for each group session, \$20 for the week 4 evaluations, \$40 for the week 8 evaluations, \$60 for the week 12 evaluations, and \$40 for each MRS scan for a maximum of \$480.

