3.5. Analysis Plan

3.5.1. Data Management and Analysis Plan: The study statistician and Healthcare Specialist will be responsible under a contract for data management and statistical analysis for the project. The Healthcare team will convert the REDCap shell from an earlier study and provide the monitoring reports, create of the final database. The study statistician will oversee the statistical analysis with the help of the Healthcare Specialist. Descriptive statistics will be generated for baseline data and distributions between the yoga intervention and walking intervention will be compared using two-sample t-tests and chi-square or Fisher's exact tests to assess effectiveness of randomization. Descriptive statistics include means and standard deviations for continuous variables and group sizes and proportions for categorical variables. All analyses will be performed at the $\alpha = 0.05$ level of significance. Should groups have unequal distributions at baseline, relevant variables will be incorporated in subsequent linear models that will be used to examine intervention efficacy. In order to address the study aims of assessing the relative longitudinal change independent variables between yoga intervention and walking intervention groups over time, data will be collected at four time points, pre-randomization, and at weeks 4, 8, and 12. Mixed linear model analyses will be performed focusing on the group x time interaction for the primary effects to be statistically modeled. These analyses will allow for inclusion of data at differing numbers of time points per subject if needed. We will examine different within-subject correlation structures for our interaction model and determine the optimal structure by comparing Akaike information criteria (AIC) values. The correlation structure that yields the lowest AIC will be adopted. Subjects who change antidepressant medications during the study will be included in intent to treat analysis, but will be co-varied for medication changes. Potential cohort effects will be statistically addressed by controlling for group profiles, including group size, breakdown by sex of attendees, instructor, group parameters such as individual or group sessions, and group cohesion/overlap.

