Hypothesis 4. a. Exploratory Concurrent Antidepressants: The yoga group but not the walking group will have a decrease in depressive symptoms regardless of antidepressant treatment at the beginning of the study.

Hypothesis 4. b. Exploratory PTSD Symptoms: If PTSD symptoms are present at screening, there will be a greater decrease in PTSD symptoms in the yoga compared to the walking group as measured by CAPS and PCL-C.

Hypothesis 4. c. Resting State Connectivity will increase over the course of the study with greater increases in the yoga group.

Hypothesis 4. d. Executive Function will increase over the study as measured by the Stroop, Digit Symbol test and fMRI activation.

3.5.2. Power Analysis for Depressive symptoms and Mood Scales: Based on the power analyses below, in order to achieve adequate power for all analyses, n=70 subjects, n=35 in the yoga and n=35 in the walking intervention must complete the interventions. Using Study 4 data in subjects with MDD in the LDG, the repeated measures ANOVA for EIFI scores from screening to the completion of the intervention did not reach statistical significance in the group of n=15 (baseline: 3.1 ± 2.2 and week-12: 3.9 ± 2.7 , $F_{1,13} = 1.097$, $p = 0.31$), a post hoc power analysis was conducted, which determined that the achieved effect size was $f = .281$, with 52% power. Based on this same effect size, an a priori power calculation was conducted, which determined that **n=35** subjects would be needed to detect significant differences for BDI-II, STAI, and EIFI scores from screening to the completion of the intervention, with effect size $f = .281$, with $< = .02$ to account for multiple comparisons, and 81% power. As the power analysis for the EIFI requires the largest number of subjects (n=70), which will be used to determine sample size. In order for 70 subjects to complete the intervention, assuming a 20% drop out, 84 subjects will be randomized.

3.5.3. Power Analysis for GABA: Consistent with our analytic plan for the longitudinal questions at-hand, we can compute the statistical power for Hypothesis II an analysis sample of **n=26** subjects in each of the study groups using the mixed linear model analogue of repeated measures analysis-of-

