4.5.2.4. Definition of Enrollment and Randomization: Participants are considered enrolled in the study when they give oral consent to the telephone interview. There is no requirement for written consent to the telephone interview. Participants are considered enrolled in screening after they sign

the written informed consent. Participants are considered randomized when they participate in their first intervention. All subjects who consent to the telephone interview are given a subject ID number and are listed on the master database that links the subject name to their subject ID. The telephone interview has two parts. The first page the telephone interview contains identifying information; this page is separated from the interview after the subject is assigned a subject ID that is used to mark the telephone questionnaire. The information in the telephone informed consent does not collect information regarding drug abuse, alcohol abuse, HIV or sickle cell.

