4.5.2.9. Recruitment: This proposal contains a randomized controlled trial in a clinical population in which 70 subjects will complete the protocol and around 420 will have a telephone-screening interview. Although this efficacy trial is not large or multi-centered, it is considered a Phase 2 trial due to the previous trial in healthy controls (Study 2) and the dosing trial in depressed subjects (Study4).

Sample size calculations, based on power analyses, require the following number of completers equally divided between the yoga and walking groups to test the hypotheses for each dependent variable: n=70 completers to test Aim 1: Depressive Symptoms and Mood Scale, n=56 to test Aim 2: GABA changes and n=68 to test Aim 3: RSA changes. To meet the criteria for each Aim/Dependent Variable 70 subjects will complete the intervention with 56 having usable MRS data. Using data from Study 4, with consideration of changes in inclusion and exclusion criteria and research setting, the following recruitment schedule will be required during a 5 year study period, which will include over 4 years of recruitment and treatment. The required total recruitment and annual requirements at each stage are as follows: telephone screen 420 total or 105/year; screening interview 173 total or 43/year; randomization 100 total or 25/year; and completers 70 total or 18/year over a 4 year recruitment period.

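### Randomisation is defined as attending the first session, not as opening the envelope, and nothing keeps allocated non-starters in the undefined intent-to-treat set

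*Protocol*

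**What the plan says.** Two sections of the Protocol, 4.5.2.4 (Definition of Enrollment and Randomization) and 4.5.2.8 (Enrollment), carry the same sentence: "Participants are considered randomized when they participate in their first intervention".

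Section 3.3.2.7 (Randomization) describes a different event: "The envelopes will be opened in sequential order at the time of randomization by a member of the staff" who is not blinded to assignment. It adds that people who want more time to decide "can be randomized within 12 days of the last screening assessment, with the interventions starting within 7 days". Table 3 also lists randomisation as a step of its own, after Scan 1.

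Section 3.3.2.8 confirms that participants know their arm: "As subjects are not blind to the intervention, there is no procedure to break the blind for clinical reasons".

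On the analysis set there is one sentence, identical in Protocol 3.5.1 and SAP D.17: "Subjects who change antidepressant medications during the study will be included in intent to treat analysis", with medication change as a covariate. Neither document says who belongs to the intent-to-treat set.

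Planned numbers appear in 3.5.2 ("assuming a 20% drop out, 84 subjects will be randomized") and in 4.5.2.9 ("randomization 100 total or 25/year; and completers 70 total or 18/year over a 4 year recruitment period").

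**The concern.** Opening the envelope is allocation; attending a session is uptake of treatment. An analyst who takes intent to treat to mean everyone randomised, and looks up that word in the Protocol's own definition section, arrives at the set of starters. People who learned their arm and then did not start would be missing from the analysis and from the drop-out count.

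That loss could plausibly depend on arm here. Participants state a preferred arm beforehand, and section 3.3.2.3 asks for it "as not being assigned to a group of choice could influence dropout rate". The other arm is offered later only to those who complete the assigned one. Exclusion after an unblinded allocation can make the analysed arms differ from the randomised ones, and it leaves the randomised denominator open to choice once arms are known.

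**Working it through.** **Text.** I compared every mention of randomisation, intent to treat and analysis population in both documents. The first-session definition appears twice, so it is not an isolated slip. Two other statements come close to filling the gap but do not. The mixed model may use unequal numbers of visits per person (3.5.1, D.17), which concerns missing visits rather than membership of the set. CONSORT is adopted in 3.2, but for quality of reporting.

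**Drop-out counts.** The plan's own figures come first. The 84 in 3.5.2 is reproduced by 70 × 1.20 = 84; dividing, 70/0.80 = 87.5, would give 88, but that is a separate matter. Loss from 84 to 70 is 14/84 = 16.7%, and loss from 100 to 70 is 30.0%.

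Now suppose the planned randomised number S counts starters, and a share q of opened envelopes never leads to a session. The documents give no q, so the values below are assumed.

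- Envelopes opened = S/(1 − q)
- Non-starters = S/(1 − q) − S
- Drop-out from envelopes = 1 − 70(1 − q)/S

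| q (assumed) | S = 84: drop-out | S = 84: non-starters | S = 100: drop-out | S = 100: non-starters |
|---|---|---|---|---|
| 0 | 16.7% | 0 | 30.0% | 0 |
| 2% | 18.3% | 1.7 | 31.4% | 2.0 |
| 5% | 20.8% | 4.4 | 33.5% | 5.3 |
| 10% | 25.0% | 9.3 | 37.0% | 11.1 |

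Example: S = 84, q = 5% gives 1 − 70 × 0.95/84 = 1 − 66.5/84 = 20.8%.

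**Treatment contrast.** Let g be the HDRS gap of non-starters over starters in an arm (positive means worse). An arm's all-allocated mean exceeds its starters' mean by q × g. For yoga minus walking, the starters-only contrast therefore differs from the all-allocated contrast by

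qW × gW − qY × gY,

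where a negative value favours yoga. With g = 5 points in both arms (assumed):

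- qY = 5%, qW = 5%: 0.25 − 0.25 = 0
- qY = 5%, qW = 15%: 0.75 − 0.25 = +0.5, against yoga
- qY = 15%, qW = 5%: 0.25 − 0.75 = −0.5, in favour of yoga

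The sign depends entirely on inputs that the documents do not supply.

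**Is redefining the set enough?** Take 50 per arm, with 3 yoga and 8 walking non-starters ending 5 points worse (all assumed). The formula gives (8/50 − 3/50) × 5 = 0.50 points. I simulated this 5,000 times with 4 visits, SD 6, within-person correlation 0.5, known covariance and a linear build-up of the gap. The week-12 change contrast was off by 0.50 with starters only. It was still off by 0.50 when non-starters were added with baseline data only. Non-starters have to contribute follow-up scores before their inclusion changes the group-by-time estimate.

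**The case against.** The strongest reply is that the harm is conditional. The first-session sentence sits among enrolment status labels in the human-subjects part, the analysis text does not refer to it, and nothing expressly excludes allocated non-starters. That is correct, and it is why no bias is claimed. It does not remove the contradiction: the only definition of the word in the Protocol is the one that drops them.

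Second, the two events may coincide. Sections 3.3.2.11 and 4.6.1.17 can be read as placing an on-site session at the randomisation visit, and 3.3.2.12 mentions a randomisation session. On that reading there may be few or no non-starters. However, 3.3.2.7 permits a gap of up to 7 days, and no section says that the first session is held at that visit.

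Third, the assumed rates may be high. In the group's earlier dosing trial (2.2.h) 30 of 32 randomised people completed, a total loss of 2/32 = 6.25%. But the documents do not say how that trial defined randomisation, and this plan allows for more loss.

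Fourth, the step from 16.7% to 30.0% comes from the 84-versus-100 discrepancy, not from this problem. That stands. The part due to non-starters is 1.7 to 8.3 points on 84 and 1.4 to 7.0 points on 100.

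Fifth, section 3.3.2.3 speaks of drop-out rather than non-starting, and its offer of the other arm rewards staying. That is fair, and it may limit the number of non-starters.

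**Conclusion.** The concern holds and should be fixed. The two definitions of randomisation conflict, the intent-to-treat set is undefined, and no text keeps allocated non-starters in it. Confidence in these three statements is high because they rest on the wording alone.

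The consequence depends on the first-session definition being the one applied and on some people not starting. On the assumed 2% to 10% non-start range, about 2 to 11 allocated people go uncounted and the drop-out rate is understated as tabulated. No size or sign is claimed for the treatment contrast: the bias is zero when the product of non-start rate and outcome gap is equal in the two arms, and can run either way otherwise.

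**What to change.** - In 4.5.2.4 and 4.5.2.8, define randomisation as the opening of the sequential envelope, to agree with 3.3.2.7.
- In 3.5.1 and SAP D.17, define the intent-to-treat set as everyone whose envelope was opened, analysed in the allocated arm whether or not any session was attended.
- Seek HDRS at weeks 4, 8 and 12 from non-starters who agree. Without this, the new definition leaves the estimate almost unchanged.
- Count non-starters as drop-outs and report them by arm in the CONSORT flow.
- State whether the first session takes place at the randomisation visit.

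The cost is wording in four places, plus up to three blinded HDRS ratings for each willing non-starter at time points the trial already runs. The reported drop-out rate may look slightly worse.

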4.6 Risk/Benefit Ratio

4.6.1. Potential Risks and Methods to be Used to Minimize Risks

4.6.1.1. Source Materials: All data collected in this study will be used specifically for research purposes. Types of data will include scores from psychological instruments, screening and monitoring forms, electrocardiogram (ECG) data and imaging data. To ensure confidentiality, all data collected will be marked with subject IDs not the subjects name, this includes paper and electronic collection. An exception to this will be serum progesterone and B-HCG levels that will be processed via the VABHCS laboratory. A master sheet with individual names and their respective code numbers will be kept in a separate locked file or password-protected computer file that can only be accessed by the research staff. The information gathered will only be used for scientific, educational, or instructional purposes. Only the research team will have access to the records. Exceptions to this rule will be made for representatives of the FDA, other U.S. government agencies, and other mandatory bodies as required by law. Forms or requests with subject names include 1) the identifiable information clinical reporting form (CRF), and 2) signed Informed Consent. These forms and any other form with subject names will be kept in a file separate from the other CRFs.

4.6.1.2. Major Depressive Disorder (MDD) Risks: There are a number of controlled treatment studies where the practice of yoga and exercise has been associated with decreased depressive symptoms. Neither the practice of yoga or exercise in the form of walking has been established as treatments for MDD. Subjects may experience increased depressive symptoms during the study. There maybe yoga or walking program outside of this study available in the VA or in the community

4.6.1.3. Magnetic Resonance Imaging (MRI) Risks: Claustrophobia while inside the magnet for the magnetic resonance (MR) assessments can potentially precipitate a panic attack in some participants. MR procedures do not involve ionizing radiation and therefore pose no significant radiation risk to participants.

However, risks do exist for persons who have metallic objects near vital structures, such as pacemakers or

aneurysm clips. Individuals with shrapnel from bombs or iron filings in the eye (mostly welders) would be at risk as well. We have a detailed MR Safety Screening Form that every person must complete before he/she receives an MR scan. The greatest risk associated with a MR exam is during the time the participant is escorted into the magnet suite or away from the magnet, as nearly all of the adverse events in MR suites have involved a ferrous metal projectile being drawn into the bore and striking the person. Our sites have very extensive safety awareness plans in place complete with detailed signage of magnetic field strength. All personnel who escort participants or patients into the scanner receive mandatory training and certification. In addition, the imaging sites have complete code carts equipped with cardiac monitors, defibrillators, suction, oxygen, and a full range of medications for any medical emergency that might occur.

4.6.1.4. Psychological Risks: Subjects may find questions about their history distressing or uncomfortable. They may feel nervous when answering psychological questions. A member of the research team will be with the participant at all times during the study sessions and will be able to answer questions concerning procedures and psychological tests. Subjects will be informed (by trained study personnel and the informed consent form) that they can decline to answer any questions, decline any procedures, or withdraw from the study at any time.

4.6.1.5. Alcohol Related Risks: As subjects will be allowed to have an Alcohol Use Disorder with up to three criteria using DSM V criteria, there is a possibility that they would come to the intervention intoxicated and could injury themselves due to intoxication.

4.6.1.6. Physical Risks: The inclusion/exclusion criteria are designed to exclude subjects who would be at risk from participation in the yoga or walking interventions. Subjects may experience muscle stiffness or discomfort from the physical components of the interventions. In Study 2, healthy yoga naïve controls were randomized to a yoga or walking intervention. In Study 4, yoga naïve subjects with MDD were randomized to two or three yoga sessions a week. Adverse events were monitored on a weekly basis during the 12-week intervention. In Study 2, minimal physical discomfort related to the interventions was reported in both the yoga and the walking group, with slightly greater discomfort reported in the yoga group. In Study 4, subjects reported muscle soreness associated with the yoga intervention (13/30 subjects) that resolved with modifications of the postures. There is minimal risk of injury during the recording of the electrocardiogram (ECG) data using the Faros 180 Sensor (Bittium USA, Inc, Bothell, WA), a hand held device powered by a 3,7 volt battery. There is some discomfort associated with the placement and removal of the electrodes. Some subjects, primarily males due to chest hair, find the removal of the ECG electrodes to be uncomfortable.

The YMCA Step Test is a standardized test that has been used for 30 years as part of the YMCA Fitness Testing and Assessment Manual. For this study a modified version of the YMCA step test (Step Test) is used as the 12-inch step has been reduced to an 8-inch step to make the procedure easier for subjects with short stature. In this protocol, the test consists of stepping up and down an 8-inch step in time to a 96 per second metronome. There are four beats to each cycle (step up foot 1, step up foot 2, step down foot 1, step down foot 2) for a total of 26 step cycles per minute. Subjects will do the YMCA Step Test for three minutes with a 6-minute rest before and after. The YMCA Step test will be done 7 times during the protocol. Subjects could find the Step-Test to be physically challenging or difficult to preform safely.

4.6.1.7. Confidentiality Risks: The yoga and walking interventions are conducted in groups. While subjects are informed that what occurs in the group is confidential, there is no guarantee that a participant may say something outside of the group that does not respect the confidentiality of the group. While source documents are marked with a subject code, there is a risk of a loss of confidentiality. Participant could be seen coming to the sessions and a person could deduce that the participant is depressed. There is a risk that the electronic data will not be secure.

4.6.1.8. Data Transfer Between Collaborating Sites: All procedures involving subjects will take place at the VABHCS. Data management and statistical analysis will be done through a contract with the Boston University School of Public Health Biostatistics, Epidemiology, Data Analytics Center and or by the VABHCS staff a Bedford VA statistician, both have worked on other VA sponsored research projects and are familiar with VA procedures regarding the handling of data. VA regulations regarding the transfer of data will be followed.

4.6.1.8.1 COVID-19 Risk: The COVID-19 pandemic presents novel risk of infection to both the subjects and research staff. A detailed response to this risk has been approved by the VABHCS IRB.

PROTECTION AGAINST RISKS

4.6.1.9. Recruitment and Informed Consent Risk Protection: Documentation will be provided to the VABHCS that the study personnel have up to date and the appropriate training in the following areas; Collaborative Institutional Training Initiative (CITI) for the ethical principals of human research, training in Good Clinical Practices (GCP), Privacy, Cybersecurity, and VA Research Data Security and Privacy. The research team will also receive training about the HIPAA regulations. This study will include children in the 18 to 21-year-old range who will be able to understand and complete the informed consent used for all subjects. The consent process will be done in a private space to insure participant confidentiality. During the consent process, all subjects will be informed that this is a research study and the use of yoga or walking for the treatment of Major Depressive Disorder (MDD) are not a conventional forms of treatment. Subjects will be informed that conventional treatments for MDD are available, such as psychotherapy, pharmacotherapy, and somatic therapies (e.g., electroconvulsive therapy, transcranial magnetic stimulation). Subjects are informed that they can change their mind about wanting to have conventional treatment at any time and that the treatment of their depression is more important than the completion of the study. Treatment options will be discussed if subjects decide not to participate in the study. The Principal Investigator's primary clinical responsibilities are at the VABHCS. In order to avoid confusion between what is treatment and what is clinical care, the informed consent will address the issue of therapeutic misconception suchthat the difference between clinical care and research will be clearly defined and the subjects will be informed that if they decline to participate in the study, there will be no effect on the clinical care that they receive. REDCap, a secure web application for building and managing online surveys and databases, will be used to manage data.

4.6.1.10. Risk of Depression: This is a treatment study with modalities that are not approved for the treatment of depression. There are alternatives to participation, such as pharmacotherapy, psychotherapy or electroconvulsive, and subjects will be informed of these other options and of their right to withdraw from the study to seek conventional treatment. Subjects are screened for risk of suicide during the screening interview with the Columbia Suicide Safety Rating (C-SSR), a widely used instrument to assess suicide risk. It is noted that the C-SSR does not provide a score stating that the assessment of suicide is a clinical decision. For this reason, other than the development of suicidal ideation with intent, the decision to withdraw a subject remains a clinical matter that is informed by the assessments built into the study. There are assessments by a psychiatrist or member of the research staff licensed to assess for suicide risk at screening, and at the weeks 4, 8, and 12 assessments using the C-SSR. Safety Data from Study 4 showed that out of 30 subjects, 9 out of 10 subjects that endorsed suicidal ideation without intent at screening no longer endorsed suicidal ideation without intent at the end of the study. No subject developed suicidal ideation with or without intent during the study. Suicidal ideation with intent with in a year of screening was exclusionary. In addition, the C-SSR evaluation were in agreement with reports of self harm on the Beck's Depression Inventory II (BDI-II), consistent with both clinical evaluation and self-report with regards to safety being accurate. In the proposed study, staff will check question 9 of the BDI-II regarding self-harm before the participant

leaves the evaluation. Participants will also have a C-SSR at screening and week 4, 8, and 12. The screening, week 4, 8, and 12 evaluations are done by research staff defined as being trained and certified to assess for safety to self and others (e.g., MD, PhD, LICSW, Master's level therapist). In addition to the monthly evaluations, subjects also fill out weekly adverse event sheets that ask if they symptoms of depression are worse or if they want to harm themselves. If increasing symptoms of depression are endorsed, this will trigger an evaluation by a research staff or the PI. Some fluctuations in depressive symptoms are expected and are not reported as adverse events unless there is a change in the level of severity as recorded in the adverse event clinical reporting forms.

4.6.1.11: MRI Risk Protection: We have a detailed MR Safety Screening Form that every person must complete before he/she receives a MR scan. All participants with ferrous metal near vital structures will be excluded from participating. At the time of the scan, participants will be asked to remove all metal objects from their person, including watches, jewelry, change, wallets, credit cards, and shoes, which will be kept by the research team in a safe location. Participants are also checked with a metal detector prior to entering the scanner. The FDA has determined that MRI machines of 4.0 or less do not represent significant radiation risk. Radio Frequency (RF) power limits will conform to the FDA guidelines defined in IEF 60601-2-33, the international standard for the safety of magnetic resonance devices intended for medical diagnosis. Participants are offered earplugs and a set of earphones to reduce the noise level. Blankets and pillows are used to make the subject more comfortable. There is a two-way audio system in the scanner through which the research team and the participant can communicate at all times. Although the experience of being in the scanner can be uncomfortable, it is our experience that a majority of subjects tolerate the procedure quite well. Subjects with clinically significant claustrophobia will be excluded from this study.

4.6.1.11.

4.6.1.12. Psychological Risks Protection: A member of the research team will be available to answer questions concerning procedures and psychological tests at all times during the study sessions. The practice of yoga or walking interventions is unlikely to cause adverse psychological reactions. The exception is that subjects with a history of trauma may find the yoga postures elicit memories of the trauma. All subjects are screened for trauma and those with a history of PTSD or PTSD symptoms are monitored for increasing symptoms during the study. The yoga instructors will be instructed on methods for addressing the special needs of trauma victims. Subject with dissociation due to PTSD could be excluded at the discretion of the Principal Investigator. In the unlikely event that a subject has an adverse experience during an intervention session, clinical staff in addition to the yoga instructors will be available during the interventions to assess subjects who are in distress. The inclusion criteria are designed to identify subjects with MDD who are not a danger to themselves or others and who are a low risk to have an adverse reaction to the interventions. As participants are Veterans and entitle to care form the VA, if there is a risk of harm to self that would require hospitalization, they will be taken to the walk in clinic or the ER for further evaluation.

4.6.1.13. Alcohol Risk Protection: In order to prevent subjects under the influence of alcohol from participating in evaluations or the interventions, all subjects will have a Breath Alcohol Concentration (BAC) done after the written informed consent and before participation in the weeks 4, 8, and 12 evaluations and at any evaluation/intervention if research staff are concerned a participant is under the influence of alcohol. If the BAC reading is not zero, participants will not be able to participate in the evaluation/intervention. If the BAC is above 0.08% or 0.08 mcrg/l, the level of legal intoxication in Massachusetts, the participant's car keys will be taken until their BAC is less than 0.08 %. The BAC will be done with a hand held Alcosensor machine Subjects will be assessed by clinical staff for safety prior to leaving if their BAC was greater than zero. These procedures are outlined in the informed consent such that participants are aware of these procedures prior to signing the informed consent.

4.6.1.14. Physical Risks Protection: To facilitate the evaluation of a subjects ability to safety comply with the interventions, they will as part of the inform consent process allow study staff to review their

VA medical records as needed. If there is a question concerning a medical problem that would be a contraindication to participation that is not in their VA medical record, the Veteran will be asked to sign a release of information to allow contact with their medical care clinicians to resolve the issue. If the Veteran declines, they maybe excluded from the study. All subjects will be assessed by a staff physician for a history of prior injuries or medical conditions that would preclude the subjects from safe participation in the yoga intervention. All subjects will have a physical examination at the screening visit as part of their safety assessment. The yoga intervention for the proposed study was piloted in Study 2 and 4 and was associated with minimal adverse events. This study uses certified yoga Instructors with Iyengar training and at least 5 years of teaching experience. Iyengar yoga is designed so that adaptations are made on an individual basis using position modifications and props such as blocks, blankets and belts. This individualized approach allows physical limitations of the subjects to be addressed and reduces and/or minimizes the risk of injury and muscle soreness. The Faros Bittium will be used in accordance with the manual. Staff that has been trained to perform the procedure will do the placement and removal of the electrodes. The Principal Investigator who is boarded in neurology and used to work at a Rehabilitation Hospital will screen subjects for difficulty with the Step Test prior to randomization.

